Drug Administration Sessions. Three 5-hour drug administration sessions of placebo, 7.5 mg, or 15 mg Δ9-tetrahydrocannabinol (THC) will be separated by at least seven days. Each session will be conducted from 9 am to 1:30 pm in comfortably furnished study rooms that resemble living room settings. Upon arrival at the laboratory, participants will provide breath and urine samples to test for recent drug or alcohol use, and pregnancy (in females). Participants will complete the Addiction Research Center Inventory (ARCI) and Profile of Mood States (POMS) and provide measures for heart rate (HR) and Blood Pressure (BP) to assess their baseline state. Participants will consume a capsule containing 0, 7.5, or 15 mg THC under double-blind conditions. The order will be randomized across subjects. Participants will be provided a snack 30 min after administration. Participants will complete the ARCI, POMS, and Drug Effects Questionnaire (DEQ) 60, 120, 180, and 240 min after taking the capsule; heart rate (HR) and Blood Pressure (BP) will be taken at the same time. During peak drug effects, participants will complete a 10-min written self-report, 5-min monologue speech task and several behavioral tasks, including the Stop Task, N-Back Task, and Time Production Task (TPT) in randomized order. At 130 min post-administration, participants will be accompanied across the hall to the EEG center for two tasks: the Auditory Oddball P300 and Flanker Interference task. After EEG measures, participants will return to the lab and subjects will be given lunch. At 240 min subjects will complete the 5 Dimensions of Altered States of Consciousness (5D-ASC) scale, the State Mindfulness Scale (SMS) and an End of Session Questionnaire before being discharged. In the interest of safety, for subjects who cannot arrange a ride home, we will pay for transportation home. After the final session, participants will be informed of the purpose of the study including the drug that they received and will be allowed to ask any additional questions about the study.

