#### Speech and Text Measures.

1. The monologue speech task (Agurto et al., *in press*; Higgins and Stitzer, 1989; Wardle et al., 2011) measures spontaneous speech, initially developed to determine how the amount of speech may be changed by acute effects of alcohol and amphetamine (Higgins and Stitzer, 1989). The task consists of a 5-min period during peak drug effects in which subjects are allowed to talk while they are alone in a room with a voice recorder. Subjects are told they are allowed to talk as much or as little as they like on any topic. All recorded speech is transcribed by a professional blind to drug condition for analysis. The primary outcome measure is the percent accuracy in classification of drug condition based on frequent word occurrences during the 5-min task.

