#### *Analytic approach*

- a. Acoustic features: Acoustic features will be extracted from five categories, including voice stability (jitter, shimmer, and voice breaks), pitch variations, spectral characterization, vowel space, and temporal features. Feature extraction involves the software Praat and Python.
- b. Semantic features: Total number of words and frequency of word occurrences will be used to compare across the drug conditions. Text derived from speech will be preprocessed with the Natural Language Toolkit (NLTK). Words will be counted from a tokenized word list, which is created by use of Treebank tagger, to identify parts of speech, and WordNet, to lemmatize words into tokens.

- c. Classification: We will use a machine learning approach to determine the number of word occurrences in text in each drug condition. This approach incorporates Random Forests, which generates decision trees based on individual word predictors.
- 2. For written self-report, participants will receive the following instructions: "For the next 10 minutes, you are asked to attend to how you are feeling right now. During this time, write down as little or as much as you like about any thoughts or sensations you are having." All writing will be converted into text for analysis. The primary outcome measure is the degree of distinction between drug conditions based on frequent word occurrences, in parallel to the 5-min speech task.

*Analytic approach*

- a. Semantic features: Total number of words and frequency of word occurrences will be used to compare across the drug conditions. Text derived from speech will be preprocessed with the Natural Language Toolkit (NLTK). Words will be counted from a tokenized word list, which is created by use of Treebank tagger to identify parts of speech, and WordNet, to lemmatize words into tokens.
- b. Classification: We will use a machine learning approach to classify the number of word occurrences in the written text. This approach incorporates Random Forests, which generates decision trees based on individual word predictors.

*Self-Report Measures.*

- 1. The Addiction Research Center Inventory (ARCI; Martin et al., 1971) is a 53-item true/false questionnaire, including a 12-item Marijuana (M) subscale specific to cannabis. We will focus our analyses on the M scale.

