Cardiovascular Measures. Blood pressure and heart rate will be monitored every 30 min using portable blood pressure cuffs, to track the cardiovascular effects of the drug, and ensure participant safety.

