2. The Flanker Interference Task (Endrass et al., 2008; Eriksen and Eriksen, 1974) is an error monitoring task involving visual stimuli. A visual target stimulus is flanked by non-target stimuli that may either be congruent, incongruent, or neutral to the target response. Experimental stimuli will be displayed with Presentation software (Neurobehavioral Systems, San Francisco, CA) on an LCD monitor placed at a comfortable viewing angle. Trials begin with a fixation mark for 1100–1700 ms. 100 ms after onset of Flanker arrows, a central target arrow will appear for 30 ms. Subjects are to indicate the direction of the central target arrow with a button press. 500 trials will be presented, with 150 being compatible trials (with congruent flanker and target errors) and 350 being incompatible trials in pseudo-random order. To maintain time pressure and ensure an adequate number of error trials, subject response times will be recorded and subjects will be prompted to move more quickly based on a moving average of the past 50 correct trials. Error-related negativities (ERNs) will be recorded. This task takes 5 mins.

Timeline:

9:00	-30	Arrival, breath and urine tests
9:15	-15	Subjective and cardiovascular measures (baseline)
9:30	0	Capsule administration
10:00	+30	Standardized snack
10:30	+60	Subjective and cardiovascular measures
10:50	+80	Written self-report
11:00	+90	Subjective and cardiovascular measures, speech and behavioral tasks
11:30	+120	Subjective and cardiovascular measures
11:40	+130	Move to CNPRU and prepare EEG for recording
12:10	+160	EEG: auditory oddball P300 and Flanker task
12:30	+180	Subjective and cardiovascular measures
1:30	+240	Subjective and cardiovascular measures, 5D-ASC, SMS, End of Session Questionnaire

**Data Analyses:** The effects of the drug on subjective, behavioral, and cardiovascular measures will be assessed with mixed analysis of variance, with the between-subjects factor of group (adolescent, adult) and within-subjects factors of drug (placebo, 7.5 mg, 15 mg THC) and time (within session). Repeated measures ANOVA will compare ERPs including P300 amplitude between THC and placebo sessions.

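### The plan gives the pre-dose ARCI, POMS, heart rate and blood pressure readings no stated analysis role; entering them as a covariate, not as a level of time, is a cheap gain in precision

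*Combined protocol and SAP*

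**What the plan says.** The Data Analyses paragraph covers subjective, behavioural and cardiovascular measures with one mixed ANOVA: age group between subjects, and "within-subjects factors of drug (placebo, 7.5 mg, 15 mg THC) and time (within session". It names no covariate and no session or order term. ERPs get one sentence: "Repeated measures ANOVA will compare ERPs including P300 amplitude between THC and placebo sessions".

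Under Drug Administration Sessions, participants complete ARCI and POMS before the capsule and "provide measures for heart rate (HR) and Blood Pressure (BP) to assess their baseline state". The Timeline has a matching row at -15 min, labelled baseline. After dosing, "Participants will complete the ARCI, POMS, and Drug Effects Questionnaire (DEQ) 60, 120, 180, and 240 min after taking the capsule", with heart rate and blood pressure at the same times. DEQ is listed only after dosing. The number of post-dose readings is not settled: the Timeline adds a set at +90 min, and the Cardiovascular Measures section says "Blood pressure and heart rate will be monitored every 30 min using portable blood pressure cuffs". Between dosing and 240 min that makes 4, 5 or 8 readings.

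On drug order the plan says only "The order will be randomized across subjects", without balancing by age group.

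**The concern.** The pre-dose reading could be a level of time, a covariate, a reference for change scores, or unused in the model. The wording allows each of these, and they do not have the same power. As a level of time, the reading pulls the averaged group x drug contrast toward zero, because the groups cannot yet differ in drug response before the capsule. As a covariate, it removes day-to-day variation in a person's starting state. The data are collected in any case, so only the model choice is at stake. Stating that choice in advance also removes discretion at analysis.

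A related question is session order. Each person attends three sessions, and any shift from first to last stays in the error for group x drug unless the model has a session term.

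**Working it through.** **Inputs from the plan.** N = 20, 10 per age group; three sessions; f = 0.403; alpha 5%; 16 participants required for 80% power (Participants section). **Assumed, because the documents do not give them:** the correlation r between single readings in one session after removing person and drug effects, equal for all pairs (compound symmetry); the session drift; within-subject SD of 1; no carryover.

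**1. The plan's own figure.** Noncentrality is f² x N x m / (1 - rho), with m repeated measures.
- m = 2, rho = 0.5, N = 16: 0.403² x 16 x 2 / 0.5 = 10.39, power 85% on F(1,14).
- m = 3, rho = 0.3, N = 16: 0.403² x 16 x 3 / 0.7 = 11.14, power 81.5% on F(2,28).

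Both sets are consistent with the stated 16; the plan gives neither m nor rho. At N = 20 they give 93% and 90%. This figure is for DEQ Feel. The plan states no power for the four measures discussed here, so an 80% reference is used.

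**2. Reference.** The group x drug test has 2 and (20 - 2) x (3 - 1) = 36 df. Power of 80% needs noncentrality 10.48. This is set for the mean of k post-dose readings, whose variance is (1 + (k-1)r)/k.

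**3. Pre-dose reading as a level of time.** The averaged signal shrinks by k/(k+1), and the variance becomes (1 + kr)/(k+1). Noncentrality is therefore 10.48 x [k/(k+1)] x [(1 + (k-1)r)/(1 + kr)].

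**4. Pre-dose reading as a covariate.** Its correlation with the session mean is R = r x sqrt(k/(1 + (k-1)r)). Noncentrality is about 10.48 x (35/36) / (1 - R²) on F(2,35); the factor 35/36 allows for chance overlap of covariate and effect.

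Results for k = 4:

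| r | noncentrality, level of time | power | R | noncentrality, covariate | power |
|---|---|---|---|---|---|
| 0 | 8.39 | 70% | 0 | 10.19 | 79% |
| 0.1 | 7.79 | 67% | 0.175 | 10.52 | 80% |
| 0.3 | 7.24 | 63% | 0.435 | 12.57 | 87% |
| 0.5 | 6.99 | 62% | 0.632 | 16.99 | 95% |

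Simulation of the covariate analysis (40,000 trials per cell) gave 78.7 / 79.9 / 86.9 / 95.2%, with type I error 4.7 to 5.2%. Break-even is r of about 0.1 between single readings, or about 0.17 between the pre-dose value and the session mean.

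**5. More post-dose readings.** At r = 0.5 the level-of-time figure is 65% with 5 readings and 70% with 8. The covariate gives 96% with 8.

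**6. Weaker pre/post correlation.** If post-dose readings correlate 0.7 with each other but only 0.3 with the pre-dose reading, R = 0.3 x sqrt(4/3.1) = 0.341. Noncentrality is 10.19/0.884 = 11.53, and power is about 84%.

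**7. Covariate plus session term, simple randomisation, no drift.** Repeated simulations gave about 75-76 / 76-78 / 80-81 / 85-86% at r = 0 / 0.1 / 0.2 / 0.3, against 80% for the plain model. Break-even moves to about 0.2 between readings (about 0.3 with the session mean).

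**8. Session term alone.** Simple randomisation, shared first-to-last shift of 0 / 0.5 / 1.0 / 1.5 SD: 80 / 77 / 71 / 59% without the term, 77-78% with it. If the age groups drift unequally: 0 versus 1 SD, 75% without and 74% with; +0.5 versus -0.5 SD, 77% and 74%. Type I error is about 5% either way. With order balanced within age group and both session and session x group fitted, power is 78-79% in all ten drift patterns tested.

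**The case against.** The strongest reply is that the readings do have a purpose, since the plan says they assess baseline state, and that time within session may already include the baseline row. That is right as far as it goes: what is missing is a stated analysis role, and one should not infer that the readings go unused. If the pre-dose reading is a level of time, the group x drug x time test can also pick up change from baseline. With four post-dose readings its power is 13 / 32 / 59% at r = 0 / 0.3 / 0.5, well below the covariate analysis.

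The size of the gain is also open to challenge. The 95% figure needs the pre-dose reading to track post-dose readings as closely as those track each other, up to 240 min after dosing. Step 6 shows how far the gain falls if it does not. The change is also more than wording, because a covariate that varies by session does not fit the classical ANOVA layout.

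Three stronger readings are tempting, and the documents do not support them.
- **The missing session term invalidates the test.** Under simple randomisation type I error stays near 5%; the only issue is precision.
- **A session term should be added regardless.** The plan gives no drift figure, and practice at the Orientation Session makes small drift plausible. With small drift and a fixed, unbalanced list, the term gains nothing or loses 2 to 3 points.
- **The power figures extend to every outcome.** The ERP sentence names no group factor, so the group x drug figures do not carry over to it. The speech outcome, "percent accuracy in classification of drug condition based on frequent word occurrences during the 5-min task", and the written one, "degree of distinction between drug conditions based on frequent word occurrences", come from Random Forest classification and are outside this point.

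**Conclusion.** The point holds as a cheap improvement for four measures, none of them primary: ARCI, POMS, heart rate and blood pressure. The plan should state the role of the pre-dose reading, and a covariate is the better choice. Over assumed correlations of 0 to 0.5 with four post-dose readings, the covariate is 9 to 33 points ahead of averaging the reading in as a level of time (79 against 70%, 95 against 62%). Against post-dose values alone it ranges from a loss of about 1 point to a gain of about 15. These sizes rest on compound symmetry and on correlations that the documents do not give, so confidence is medium. DEQ Feel, which has no listed pre-dose reading, and the once-per-session tasks gain nothing from the covariate.

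The session term is a secondary, conditional matter. Under simple randomisation it breaks even near a shared first-to-last shift of 0.5 SD and helps only if shared drift is larger.

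**What to change.** 1. For ARCI, POMS, heart rate and blood pressure, analyse post-dose values only and keep the post-dose time points as the time factor. Enter that session's pre-dose value as a covariate, expressed as the deviation from the person's own mean pre-dose value. Fit a linear mixed or subject-fixed-effect model, so that group x drug is still judged against session-to-session variation within person. State which post-dose times count, since the sections differ. Cost: a model change and 1 to 2 points of power if the correlation is zero; no new data or visits.

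2. Optional, only if the randomisation list is still open: balance drug order within each age group (one full block of the six orders, then four different orders drawn at random; exact balance is impossible with 10 per group). Add session and session x group to the models that test group x drug. Cost: 4 of 36 error df, about 1 point of power with no drift. Do not balance without the session terms: at a 1.5 SD shared shift that gives 1.3% type I error and 57% power.

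3. If the list is already fixed by simple randomisation, treat a session term as a judgement call, and record the decision and its reason before unblinding. Omit session x group in that case; with no drift the two terms together cost about 5 points.

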## Protocol

Title: Age-Related Effects of THC (“Effects of drugs on behavior – ART” on the consent form)

Principal Investigator: [name], Ph.D.

Co-Investigators: [name]. and [name].

**Objectives:** **1)** To determine whether adolescents (defined here as ages 18-20) are at greater risk to acute oral 7.5 and 15 mg  $\Delta 9$ -tetrahydrocannabinol (THC) intoxication than adults (defined here as ages 30 to 40), **2)** to develop a sensitive behavioral measure to detect intoxication levels of THC, and **3)** to determine whether age-related drug effects are detectable using electroencephalography (EEG).

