Our central hypotheses are 1) that the subjective, behavioral, and physiological responses to acute THC will be greater in adolescents, including reductions in EEG activity during task performance, and 2) that speech and text analyses will be sensitive indices of acute THC intoxication across dose and age. We and others have used analysis of speech production to detect effects of drugs, using measures of both production and content (Baggott et al., 2015; Bedi et al., 2014). To our knowledge, speech and text analyses have not been used to study THC. Our hypotheses will be tested using a well-established regimen of oral 7.5 and 15 mg THC administration in the laboratory (Childs et al., 2017; Pabon and de Wit, 2019; Wardle et al., 2015).

**Significance & Innovation:** Cannabis use is widespread among adolescents and young adults with over 11 million people ages 18-25 having consumed cannabis in the past year (2015) in the United States (National Institute on Drug Abuse). Furthermore, the average age of onset is 19 years of age (National Survey on Drug Use and Health). Cannabis products are increasingly accessible to young adults in the United States, a trend tied to increased use (Ter Bogt et al., 2014). For example, after cannabis was legalized in Colorado in 2011, past year cannabis use increased from 39% to 49% for ages 18-25 through 2017 (National Survey on Drug Use and Health). The consequences of long-term cannabis use are more severe in adolescents, and there is evidence that chronic use of cannabis in adolescents is associated with impaired neural maturation (Chadwick et al., 2013; Coffey and Patton, 2016). However, it is not established whether adolescents are more or less sensitive to the short-term effects of acute THC intoxication. Preclinical studies consistently show that adolescent rats are more sensitive to the acute effects of THC than adult animals (Cha et al., 2006; Quinn et al., 2008; Wiley et al., 2007). The period of sensitivity coincides with a neurodevelopmental period when cannabinoid receptors are most densely expressed in both rodent and human cortex (Choi et al., 2012; Gee et al., 2016; Heng et al., 2011; Long et al., 2012; Meyer et al., 2018). Therefore, human adolescents may also be more sensitive to the acute effects of THC, and under certain circumstances this may increase their risk for adverse effects such as psychosis and behavioral impairments, or likelihood of abuse.

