A third goal is to determine whether THC alters EEG patterns, and whether this is related to age. THC is known to affect neural responses as measured by EEG from oscillatory power to evoked related potentials (ERP) (Skosnik et al., 2016). (For instance, oral, smoked, and intravenous administration of THC reduce the amplitude of the P300 waveform (D'Souza et al., 2012; Ilan et al.,

2005; Roser et al., 2008; Stadelmann et al., 2011; Theunissen et al., 2012). The P300 is a positive waveform that peaks 300 ms after a stimulus and is related to attention and working memory. Another study showed that vaporized THC (22 mg) reduced the error-related negativity (ERN) in frequent cannabis users. ERN is an ERP with negative polarity that corresponds to a participant's recognition of error during an error-monitoring task (Kowal et al., 2015). Although THC is known to disrupt gamma (30-80 Hz) and theta (4-7 Hz) oscillations (reviewed by Skosnik et al., 2016), in this study, we will focus specifically on the P300 and ERN. Electrophysiological measures are valuable because they provide a sensitive direct measure of neural activity and can be used to examine drug effects, and age-related variations in drug effects, in relation to both mood and cognitive performance.

**Research Design:** We will use a combined within and between subject design to examine whether healthy, young men and women (aged 18 to 20) are more sensitive than older participants (aged 30 to 40) to the acute effects of THC. Healthy occasional cannabis users in the two age groups will participate in three laboratory-based sessions spaced at least seven days apart, in which they will receive capsules containing placebo, 7.5 mg THC, or 15 mg THC under double-blind conditions. For each session, participants will complete self-report questionnaires of subjective effects, and cardiovascular measures will be obtained at regular intervals. They will complete speech, behavioral, and electroencephalogram (EEG) tasks once each session, at the time of expected peak effect.

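### The planned ERP analysis has no age-group term, so Objective 3 (age-related THC effects on EEG) has no test

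*Combined protocol and SAP*

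**What the plan says.** **The aims.** The third objective, on the opening page of the protocol, is "to determine whether age-related drug effects are detectable using electroencephalography (EEG"). The background restates it in two parts: "A third goal is to determine whether THC alters EEG patterns, and whether this is related to age". The first central hypothesis gives a direction, namely that "physiological responses to acute THC will be greater in adolescents, including reductions in EEG activity during task performance". For the endpoints, the protocol says that "we will focus specifically on the P300 and ERN".

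**The analysis.** Data Analyses has two sentences.
- The first reads "The effects of the drug on subjective, behavioral, and cardiovascular measures will be assessed with mixed analysis of variance". For that model it lists age group as the factor between subjects, and drug (three levels) and time as the factors within subjects.
- The second deals with EEG: "Repeated measures ANOVA will compare ERPs including P300 amplitude between THC and placebo sessions".

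The EEG Measures section describes recording, filtering and the two tasks. It contains no statistical model. No other section gives an ERP analysis by age.

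**The concern.** Whether a drug effect depends on age is a group x drug question. The plan states that model for every class of measure in its first analysis sentence, and EEG is not among them. The ERP sentence names one comparison, THC against placebo. It names no group factor and no interaction, and it does not say whether the 7.5 mg and 15 mg sessions are pooled or kept apart.

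An analyst who followed this text would report an average THC effect over both ages and could draw no conclusion about age. A real age difference would be averaged into the drug effect, and the rest of it would go into the error term. If the age test were added later, its form (doses pooled or separate, which contrast, ERN included or not) would be chosen after the data were available.

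**Working it through.** **1. Aims against planned tests**

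| Question | Term needed | Planned for ERPs? |
|---|---|---|
| Does THC alter the ERP? (first half of the third goal) | drug | Yes |
| Does the THC effect differ by age? (Objective 3; second half of the third goal; first central hypothesis) | group x drug | No |

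The conclusion follows from this comparison alone. The figures below only show its size.

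**2. The plan's own power figure**

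The Participants section gives f = 0.403 for the group x drug interaction on the Drug Effects Questionnaire "feel" item, alpha 5%, at least 80% power and a required N of 16. The number of repeated measures (m) and their correlation (rho) are not stated. For the within-between interaction with two groups, lambda = f² x N x m / (1 − rho), with df = (m − 1) and (N − 2)(m − 1).
- m = 2, rho = 0.5: lambda = 0.1624 x 16 x 2 / 0.5 = 10.39, df (1, 14), power 0.850. N = 14 gives 0.790.
- m = 3, rho = 0.3: lambda = 0.1624 x 16 x 3 / 0.7 = 11.14, df (2, 28), power 0.815.

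N = 16 can therefore be reproduced under plausible unstated settings. It concerns a self-report item, and no ERP effect size or power is given anywhere.

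**3. What the drug-only comparison can see**

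Take the THC-minus-placebo change for one ERP, with SD 1 within each age group and 10 per group.
- Effect d in one group and 0 in the other: the average is (10 x d + 10 x 0)/20 = d/2. With d = 1.32 this is 0.66.
- Effect 0.66 in both groups: the average is also 0.66.

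The point estimates have the same expectation. The test statistics differ, because ignoring group inflates the variance in the first case. The expected sample variance is (18 + 1 + 20 x 0.66²)/19 = 1.46, an SD of 1.21 instead of 1. That loss of precision does not reveal an age effect, since larger ordinary variability would look the same.

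The group comparison of change scores does separate the cases. For a difference of 1.32 SD, the noncentrality is 1.32 x √5 = 2.95 on 18 df, which gives power 0.797. Simulation gave 79.6% rejection when the effect is in one group only and 4.9% when it is uniform.

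An extreme case has the groups 1.32 SD apart with a zero average effect (40,000 runs). The drug-only test rejects in 2.0% of trials and the interaction test in 79.9%.

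**4. What the corrected test can detect at N = 20**

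- Three drug levels: df = (2, 36). Power of 80% at alpha 5% needs lambda = 10.48. Partial eta-squared = 10.48/(10.48 + 36), about 0.23, with complete data and sphericity. With a sphericity epsilon of 0.75 or 0.5 it is about 0.26 or 0.33.
- One THC-placebo contrast, 10 against 10: detectable age difference about 1.32 SD of the change score.
- Power over assumed effect sizes (m = 3, rho = 0.5, lambda = 120 x f²): 0.14 at f = 0.10, 0.45 at 0.20, 0.65 at 0.25, 0.81 at 0.30, and 0.97 at 0.403 if the questionnaire value applied to an ERP.

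The two effect-size scales must not be mixed. Lambda = 10.48 corresponds to f = √(10.48/36) = 0.54 on the partial eta-squared scale, and to f = √(10.48/120) = 0.30 on the scale with rho = 0.5.

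**The case against.** The strongest reply is that the ERP sentence is incomplete rather than exclusive. A repeated measures ANOVA can carry a between-subjects factor, the study is described as a combined within- and between-subject design, and the age question for EEG is stated three times. On that reading the group term is intended and merely unwritten. The intent is indeed clear, and nothing shows a decision to ignore age. But the sentence immediately before names group, uses a different model label and lists the measures it covers without EEG. The only ERP comparison stated is THC against placebo, so the plan as written has no test of the age question.

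Several narrower points stand:
- The planned ANOVA does test the first half of the third goal, whether THC alters EEG.
- The text is ambiguous on dose. It does not say that the two doses are pooled.
- The equality in the one-group example holds for the expected point estimate, not for the p-value.
- The 2.0% against 79.9% contrast supposes that the ages respond in opposite directions, whereas the protocol expects a larger reduction in adolescents.
- The primary outcome is the "feel" rating, and its group x drug analysis is specified.

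The last point bears on priority. A numbered objective without a test still needs correction before analysis, particularly when one sentence supplies it.

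**Conclusion.** The concern holds. None of the planned ERP tests addresses Objective 3 or the age part of the EEG hypothesis, because the stated analysis has no group x drug term. This rests on the wording of Data Analyses set against the stated aims and depends on no assumed figure.

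The illustration of its size (a one-group effect of 1.32 SD indistinguishable on average from a uniform 0.66 SD, with interaction rejection of about 80% against 5%) assumes 10 complete participants per group, normal change scores with equal variance, and alpha 5%. The detectable partial eta-squared of about 0.23 also assumes sphericity. The data needed to answer the objective will be collected from both age groups, so the defect lies in the analysis text and not in the design. It should be corrected before the ERP data are analysed.

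**What to change.** Replace the ERP sentence with wording such as:

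*P300 amplitude (oddball task) and ERN amplitude (Flanker task) will each be analysed with age group (adolescent, adult) as a between-subjects factor and drug (placebo, 7.5 mg, 15 mg) as a within-subjects factor. The group x drug interaction is the test of Objective 3. The drug main effect addresses whether THC alters the ERP.*

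Keep the two doses as separate levels. In the same place:
- name the follow-up contrasts (the age difference in each dose-minus-placebo change), since the hypothesis is directional and a 2-df interaction is not;
- say how the two ERP endpoints are handled together and how departures from sphericity are treated;
- state that N = 20 was sized on the questionnaire item and not on an ERP, so a non-significant interaction does not show that age makes no difference.

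The cost is a few sentences and no new data. The group term uses 1 df between subjects and the interaction 2 df within subjects.
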